## **2. LIST OF ABBREVIATIONS**

CCI	Charlson Comorbidity Index
COPD	Chronic obstructive pulmonary disease
CTMF	Clinical Trial Master File
ACAAI	American College of Allergy, Asthma and Immunology
ACT	Asthma control test
ATS	American Thoracic Society
BI	Boehringer Ingelheim
EMR	Electronic Medical Records
EMA	European Medicines Agency
ERS	European Respiratory Society
FDA	Food and Drug Administration
GPV	Global Pharmacovigilance
HCRU	Health Care Resource Utilization
HIPPA	Health Insurance Portability and Accountability Act
ICD	International Classification of Diseases
ICS	Inhaled Corticosteroid
LABA	Long-acting beta-agonist
LTRA	Leukotriene Receptor Antagonists
PSM	Propensity Score Matching

#### 4. ABSTRACT

Name of company: Boehringer Ingelheim			
Name of finished medicinal product: Spiriva Respimat 1.25 mcg			
Name of active ingredient: Tiotropium Bromide® 1.25 mcg			
Protocol date: 18 Feb 2019	Study number: 0205-0543	Version/Revision: 1	Version/Revision date: NA
Title of study:	The effectiveness of Tiotropium Add-on therapy using a Real-world cohort of patients with Asthma		
Rationale and background:	While asthma imposes a substantial burden on the healthcare system, the cost of uncontrolled asthma is more than double that for controlled asthma patients. Asthma therapy involves a stepwise approach depending on control and severity levels. To better guide treatment decision making, it is imperative to understand the impact of different treatment choices on health outcomes in a real-world setting for patients taking ICS/LABA combinations.		
Research question and objectives:	To evaluate the effectiveness of add on therapy with Tiotropium Respimat® compared to increasing the dose of ICS in patients with a diagnosis of Asthma and on ICS/LABA therapy.		
Study design:	Retrospective cohort data analysis of patients with asthma prescribed with ICS/LABA therapy. Patients will be followed after the date of first ICS/LABA prescription and those prescribed Tiotropium Respimat® will be classified under the ‘Tio’ group while the rest will be under the ‘NonTio’ group. Outcomes will be compared between these two groups.		
Population:	Asthmatics 6 years and above and on ICS/LABA at baseline		
Variables:	Baseline measures will include patient demographics, medications, control status, comorbidities, resource use, eosinophil levels (if available), ACT score (if available).		
Data sources:	IMS Pharmedics (IMS or Database I); EMRClaims+ (Database II)		
Study size:	>6,300 (expected)		
Data analysis:	Propensity Score Matching will be conducted using baseline characteristics in order to ensure as much similarity between the two groups. Time to first exacerbation (primary outcome) will be compared between the two groups descriptively, as well as using Cox PH modelling techniques. Secondary outcomes will include rate of exacerbation, proportion of patients with exacerbation, health care resource use and cost during follow-up,		
Milestones:	Study protocol; Draft Results; Final Results		

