### **9.1 STUDY DESIGN**

Data extraction from both databases (I and II, see [section 9.4](#)) will be conducted by

. All patients will be required to have a prescription for ICS/LABA therapy [e.g. Advair (Diskus and HFA), Airduo, Breo, Dulera, or Symbicort]. The date of the first prescription of ICS/LABA within the study period (Jan 1st 2016 to Nov 30th 2018) will be defined as ICS/LABA-initiation (ICS/LABAi) date. This baseline cohort will then be followed to identify two cohorts (two arms of the study). One cohort that receives a prescription for Tiotropium Respimat® 1.25 mcg (on top of baseline ICS/LABA) will be classified as the ‘Tio’ group, and the second cohort that receives a “step-up” from baseline low-dose ICS/LABA to medium/high dose ICS/LABA or from baseline medium dose ICS/LABA to high dose ICS/LABA or an additional prescription/refill of high-dose-ICS/LABA following the first prescription of baseline high dose ICS/LABA within the study period, will be classified as the ‘NonTio’ group. The date of the first prescription for Tiotropium Respimat® 1.25 mcg in the ‘Tio’ group will be defined as the index date for the ‘Tio’ group. Similarly the date of the first prescription for a “step-up” from baseline low-dose ICS/LABA to medium/high dose ICS/LABA or from baseline medium dose ICS/LABA to high dose ICS/LABA or an additional prescription/refill of high-dose-ICS/LABA following the first prescription of baseline high dose ICS/LABA (evidenced by at least 90-days of prescription utilization) within the study period will be defined as the index date for the ‘NonTio’ group.

Patients will be required to have a minimum follow-up period of 30 days after the index date for the analyses of the primary endpoint with no limit on the maximum period (this 30-day minimum follow-up period requirement will be waived in a sensitivity analysis). Subject to sample size requirements, patients will be required to have available records for at least 12 months prior to the index date to ensure no prior use of Tiotropium Respimat® and to establish baseline patient characteristics. This 12-month period prior to the index date will be defined as the pre-index period.

Figure 9.1.1 Study Design

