## **9.7 DATA ANALYSIS**

### **9.7.1 Main analysis**

We will provide the sample attrition at each step of the inclusion-exclusion criteria as well as a baseline demographic and comorbidity breakdown. We will provide a comparative breakdown in baseline measures for the unmatched and matched cohorts to assess if PSM eliminated baseline differences. For the primary endpoints analysis, we will calculate the time to first exacerbation per patient and compare it between the two groups (Tio vs. NonTio). For secondary endpoint analyses we will compare the rate of exacerbation, proportion of patients with exacerbations after 6 months and one year (based on Kaplan Meier estimates), HCRU and average cost during follow-up and compare them between the two groups (Tio vs. NonTio).

The primary outcome of the study will be analyzed using Cox proportional hazard modelling. The secondary outcome of rate of exacerbation per patient will be analyzed using negative binomial regression. This technique works on the assumption that the rate of exacerbation varies among every subject in the study ([P16-06846](#)). Also this model accounts for overdispersion of data which is likely to happen due to variability between the patients. Balance in covariates will be checked after matching. If PSM was able to balance all observed baseline characteristics, the regression models for outcomes will be limited to the databases (IMS and EMR) and to the key independent variable of interest (namely Tio use vs. ICS/LABA dose increase) and model overfitting is not, therefore, of concern. However, if there are unbalanced baseline characteristics, we will include these characteristics in the regression as covariates. For regression model covariate selection we

will also estimate the multicollinearity of covariates by assessing their correlations of independent variables. For example, if comorbidities from the specific list are also included in CCI, they will only be included in the CCI.

In order to handle missing data, in the PSM we will create a category variable (‘missing data’) for each covariate to ensure that patients with that variable and without that variable are respectively matched. Patients with missing prescription data required for classification of the treatment groups will be excluded. Patients with missing lung function scores and ACT scores at baseline and in the follow up period will be excluded from these respective secondary analyses.

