## **9.10 OTHER ASPECTS**

The IMS® PharMetrics Plus database is comprised of adjudicated claims for more than 150 million unique enrollees across the US. Enrollees with both medical and pharmacy coverage in 2012 represented 40 million active lives. Patients in the majority of three-digit zip codes and in every metropolitan statistical area of the US are represented, with coverage of data from 90% of US hospitals, 80% of all US doctors, and representation from 85% of the Fortune 100 companies. Because the database is constructed from a variety of geographic regions and employer groups, the database maintains a level of diversity while representing the overall trend in commercial health plan coverage. The underrepresentation of the population aged 65 years and older may affect external validity in the case of Medicare, Medicare Advantage or Medicaid patients.

EMRClaims+®, will offer lung function results, Asthma Control Test (ACT) scores, as well as eosinophil counts for asthma patients in addition to administrative data. EMRClaims+® is an integrated health services database containing more than 20 million EMR across 7 states in the Midwestern region of the United States. The database includes administrative insurance claims across approximately 690,000 lives linked to an overlapping healthcare provider database of EMR, including laboratory values, and provider billing files. This data source uniquely provides a strong-level of internal validity since two separate sources (EMR and administrative data) cross reference unique patient identifiers. In the event of discrepancies between administrative files and EMR data (or for uncertainty about disease classification), manual evaluation of the individual patients' medical records is conducted to provide resolution based on access to the complete patient medical history in the EMR.

The databases do not have the capability to uniquely identify members who disenroll and re-enroll; consequently, these individuals are assigned a new identifier and may be represented in the data as two unique subjects. It is also possible that a patient may be in both cohorts. Both possibilities will be checked using zip codes. If two patients are suspected of being the same, only the data with the longer follow-up period will be used.

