## 9.12 BIAS

### Channeling Bias Mitigation

Introduction of channeling bias in this study is highly likely using retrospective claims data based on asthma medication use; patients between the two cohorts may differ in baseline control and severity levels. On aggregate, patients for whom Tiotropium Respimat® 1.25 mcg was added (vs NonTio) are likely to be less well-controlled and more severe both at baseline and during the follow up period. Absent a method to control for this channeling bias, it is likely that placing sicker patients in the Tiotropium Respimat® 1.25mcg group will confound an accurate comparison of cost, resource use, and other outcomes between the groups. Two design features of our study will help mitigate this bias. First, our comparison (NonTio) group will be required to step-up their baseline ICS/LABA dose or have an additional prescription/refill of high-dose-ICS/LABA following the first prescription of baseline high dose ICS/LABA within the study period. Second, we will use Propensity Score Matching (PSM) to match patients on key measures of disease control and severity as listed in [Table 1](#), such as demographics, Charlson Comorbidity Index (CCI) score, specific comorbidities, number of prescriptions (overall and asthma-related medications). This baseline matching strategy will be particularly important to ensure that patients in the TIO group who have a corresponding increase in their ICS dose at or prior to the date of their TIO prescription (for example, if the patient has an exacerbation), will be matched to a corresponding NonTIO patient in terms of increased ICS dose or additional ICS prescription. It should be noted that after the prescription index date for both Tio and NonTio patients, we anticipate changes in ICS medication for patients in both cohorts. These ICS medication changes reflect patient

outcomes in the follow-up period, where patients who encounter exacerbation in either group are likely to see a change in the ICS dose.

As a result, post-index period ICS medication changes will not alter the classification of patient groups nor will it be the basis for exclusion of these patients.

We will conduct 1:2 matching using a nearest neighbour matching approach with a radius of  $0.2 * SD(\log(P))$ . This will be conducted in both databases (IMS: Cohort I and EMRClaims+: Cohort II) separately.

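### The plan gives no rule for a NonTio patient who later starts tiotropium, so an event after the index date could decide who stays in the comparator group

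*Combined protocol and SAP*

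**What the plan says.** Three places in the combined protocol and SAP bear on group membership.

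- **Section 4 (Abstract, study design).** Patients are followed from the first ICS/LABA prescription, and "those prescribed Tiotropium Respimat® will be classified under the ‘Tio’ group while the rest will be under the ‘NonTio’ group". No time point relative to a NonTio index date is given.
- **Section 9.1.** "This baseline cohort will then be followed to identify two cohorts (two arms of the study"). NonTio is defined by a step-up in ICS/LABA dose, or by a further high-dose prescription, with its own index date. Tio use is checked only in the period before index. Follow-up has no maximum.
- **Section 9.12.** The matching is meant to deal with "patients in the TIO group who have a corresponding increase in their ICS dose at or prior to the date of their TIO prescription". The same section says that "post-index period ICS medication changes will not alter the classification of patient groups" and that such changes do not exclude a patient. Starting Tio after a NonTio index date is not mentioned.

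The eligibility list in section 9.11 and the analysis text in section 9.7.1 contain no rule on switching or censoring at Tio start. The study-design figure (Figure 9.1.1) could not be read in the text available.

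**The concern.** With open-ended follow-up, some patients may step up their ICS/LABA dose, qualify as NonTio, and be prescribed Tio later. A programmer must then keep the patient in NonTio, censor at the Tio start, move the patient to Tio, or enter the patient in both arms. The text does not choose, so two programmers could build different comparators for the primary analysis.

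Moving the patient is the option that causes harm. NonTio would then be defined partly by never receiving Tio in the future, which is not known at the index date. If Tio is started more often after an exacerbation, removal takes out NonTio patients together with their events, and the comparison is biased against Tio. If Tio is started less often after an exacerbation, the bias favours Tio. If the two are unrelated, there is none. The propensity score uses only pre-index variables and cannot correct selection on what happens afterwards. Section 9.12 makes the first direction plausible, since it gives an exacerbation as an example of what leads to an ICS increase at or before the Tio prescription, but it does not establish it.

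**Working it through.** **1. The passages side by side.** Take a patient with a qualifying step-up in month 3 and a first Tio prescription in month 9.

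- Abstract: Tio, because Tio was prescribed after the first ICS/LABA prescription.
- Section 9.1 alone: meets the NonTio definition at month 3 and the Tio definition at month 9. Nothing makes the groups exclusive or ranks them.
- Section 9.12: may be counted as Tio, since the ICS increase came before Tio. The protection against reclassification covers ICS changes only.

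**2. The plan's own figures.** Section 9.5 gives 2,100 Tio and 4,200 NonTio patients, NonTio hazards of 0.012 and 0.028 per month, Tio hazards of 0.0096 and 0.0224 (ratio 0.80), and power of 77% and 98%. Neither alpha nor a common follow-up is stated. With two-sided 0.05 and 10 months assumed, the Schoenfeld formula gives 77.5% (667 events) and 97.9% (1,447 events). Both figures are reproduced; they serve here only to cost the fix.

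**3. Effect of removal.** Assumptions: exponential times, 12 months, true hazard ratio 1. Let λ be the monthly hazard, a the share of NonTio exacerbators removed and b the share of the others removed.

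- Exacerbation share: p = 1 − exp(−12λ) = 13.4% at 0.012 and 28.5% at 0.028.
- Person-months per original patient: others O = 12(1 − p); exacerbators E = p/λ − O. At 0.012, O = 10.391 and E = 0.785.
- Apparent Tio/NonTio hazard ratio = λ[(1 − a)E + (1 − b)O] / [(1 − a)p].

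The ratio is 1 when a = b, that is, when the share of later Tio starters who had exacerbated first equals p. Above p the bias is against Tio; below p it favours Tio.

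**4. Tying the shares to the 2,100 Tio patients.** The documents give no switching rate and no NonTio pool size. Assume a share s of 10-25% of the 2,100 come from NonTio, so m = 2,100s = 210 to 525, and a share f of these had exacerbated first. Then a = mf/(pool × p) and b = m(1 − f)/(pool × (1 − p)).

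Example: pool 20,000, s = 25%, f = 1, λ = 0.012. Then a = 525/(20,000 × 0.1341) = 0.196 and b = 0. The ratio reads 0.012 × (0.804 × 0.785 + 10.391)/(0.804 × 0.1341) = 1.23. With a pool of 100,000, a = 0.039 and the ratio reads 1.04.

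A true ratio of 1 reads, over both hazards and s = 10-25%:

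| Exacerbated before Tio | Pool 100,000 | Pool 20,000 |
|---|---|---|
| All | 1.01-1.04 | 1.03-1.23 |
| Half | 1.00-1.02 | 1.01-1.09 |
| None | 0.99-1.00 | 0.97-0.99 |

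These are averages over the pool; the matched subset could differ.

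**5. Does fixing membership at index work?** In a simulation where 5% of non-exacerbators start Tio within 12 months and the rate triples after an exacerbation (both assumed), removal reads 1.05-1.06 for a true 1 and 0.84 for a true 0.80. Keeping the patients and censoring at Tio start reads 1.00 and 0.80.

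**The case against.** The strongest reply is that removal is an inference. The abstract sentence is a summary: taken literally, it also drops the step-up requirement. Section 9.1 gives NonTio its own index date, and none of the criteria in section 9.11 excludes a patient for later Tio, so those two sections alone leave the patient in NonTio. Section 9.12 explains matching and does not say that an earlier NonTio record is deleted; an ICS increase on the Tio date itself need never have qualified as NonTio. Its stated principle, that post-index ICS changes do not reclassify or exclude, points away from removal. The unread figure might also settle the point. All of this stands as far as it goes: a reader might infer that the plan instructs removal, and it does not. What remains is that the abstract points the other way, and no readable text resolves the two.

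A second reply concerns size. A reader might assume that a tenth or a fifth of exacerbators are removed and quote large biases for any pool. Many such scenarios do not fit section 9.5. Removing 10% of exacerbators and 5% of others from a pool of 100,000 takes 5,671 to 6,427 patients (100,000 × [0.10p + 0.05(1 − p)]), more than the whole Tio group of about 2,100. Only the figures tied to that group are used here. Section 9.4 describes about 150 million lives in Database I, so a large pool, and hence a small bias, is possible.

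A reader might also see a further contradiction in section 9.10: "It is also possible that a patient may be in both cohorts", and "If two patients are suspected of being the same, only the data with the longer follow-up period will be used". Applied to the arms, that rule would usually keep the earlier NonTio record. But it concerns duplicate identifiers checked by zip code, and section 9.12 uses the word cohort for the databases as well. It adds little either way.

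**Conclusion.** The gap stands and should be fixed. The abstract and section 9.12 can be read to move a NonTio patient to Tio because of a later prescription; section 9.1 can be read to keep the patient; the readable text does not decide. Under the first reading, membership of the primary comparator depends on post-index events.

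The documents do not show that the study is biased, by how much, or in which direction. Under the assumptions above, a true hazard ratio of 1 reads about 0.99-1.04 with a pool of 100,000 and 0.97-1.23 with 20,000. The upper end of 1.23 needs a small pool, a quarter of Tio patients coming from NonTio, all of them after an exacerbation, and the lower hazard. With a large pool the bias is small. The certain part is the ambiguity; confidence that the bias is material is moderate at most.

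**What to change.** Reconcile the abstract with sections 9.1 and 9.12, and state that NonTio membership is set only by data up to the NonTio index date, so that a later Tio start does not remove the patient. Then:

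1. Pre-specify two analyses of follow-up after a later Tio start: as-assigned, and censored at Tio start. Which is main and which is sensitivity is the sponsor's choice. As-assigned mixes Tio exposure into NonTio; censoring may be informative.
2. If one patient can contribute to both arms, do not match the two records to each other, count no event twice, and use patient-clustered variance. In the as-assigned analysis, one way to avoid double counting is to leave out that patient's Tio record, which changes the Tio group in that analysis.
3. Section 9.1 says "Patients will be required to have a minimum follow-up period of 30 days after the index date for the analyses of the primary endpoint". Count these days on available records, not on time to Tio start; otherwise early switchers are dropped again.
4. Section 9.7.1 says "We will provide the sample attrition at each step of the inclusion-exclusion criteria". Add the number of NonTio-eligible patients who later start Tio and how many exacerbated first. This would show whether the problem is material.

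**Cost.** Protocol wording and modest programming. Extraction is still described as future, and Tio fill dates after the NonTio index date must be kept. The 1:2 matching stays.

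*Power under censoring.* If 5-20% of NonTio patients are censored at random times, about 2.5-10% of NonTio events are lost. With Tio to NonTio events at 0.4 to 1 (half the patients, ratio 0.80), a loss L multiplies the information by 3.5/(1/(1 − L) + 2.5). At L = 10% this is 0.969, and 77% power becomes 75.7%; at 2.5% it becomes 76.7%. The cost is about 1 point at most.

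*Informative censoring.* In a simulation with 30% high-risk patients (hazard doubled) who start Tio 2-4 times as often (all assumed), censoring reads a true 1 as 1.00-1.01 when 6-9% of NonTio start Tio and as 1.02-1.05 when 25-32% do. Removal reads 1.01-1.02 and 1.03-1.10 in the same cases.

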## **5. AMENDMENTS AND UPDATES**

*None*

## **7. RATIONALE AND BACKGROUND**

While asthma imposes a substantial burden on the healthcare system, the cost of uncontrolled asthma is more than double that for controlled asthma patients (ACAAI). The European National Health and Wellness Survey ([P19-00715](#)) and the Real-world Evaluation of Asthma Control and Treatment (US) ([R16-0701](#)) survey both found that 55% of asthma patients were uncontrolled, even among those who are treated. Asthma therapy involves a stepwise approach depending on control and severity levels. Uncontrolled asthma, which may present regardless of severity level, results in exacerbations, use of systemic corticosteroids, and declined lung function ([P14-03600](#)). When asthma is not controlled, guidelines recommend increased ICS dose, and use of ICS in combination with long-acting  $\beta$ 2-agonists (LABA), and/or other add-on therapy, including leukotriene receptor antagonists (LTRA), antibody biologics or oral corticosteroids. The ERS/ATS guidelines ([P14-03600](#)) define severe asthma as that which remains uncontrolled despite use of high dose ICS as well as controller medications or systemic corticosteroids. Uncontrolled asthma is associated with an increased risk of exacerbation, which results in impaired lung function, reduced patient quality of life and increased health care resource use. To better guide treatment decision making, it is imperative to understand the impact of different treatment choices on health outcomes in a real-world setting for patients taking ICS/LABA combinations.

The intended audience will be health systems, payers and prescribers. The results of the study will be used to provide evidence of the effectiveness of tiotropium as add-on therapy in reducing exacerbations, reducing the increased dosing of current medications and health care resource utilization for their asthma patients.

In September 2015, the FDA approved Spiriva Respimat for Inhalation Spray for the long-term, once-daily, maintenance treatment of asthma in patients 12 years of age and older (6 years and above approved in Feb 2017).

